## 7.3 Medicis Midface Volume Scale (MMVS)

MMVS is a Four-Point scale assesses the fullness of the midface from Fairly Full (1) to Substantial Loss of Fullness (4) as described below. A validation study concluded that the accuracy of this assessment tool was acceptable for use in assessing correction of midface volume loss and/or contour deficiency. The blinded evaluator will rate the subject's right and left midface for severity of volume deficiency using the MMVS at screening, baseline, 6, 9, 12, 18 and 24 months in Group A and Treatment Group, and at screening, baseline 6, 9 and 12 months in Control Group. The treating investigator will do the MMVS evaluation at all visits in each group. The blinded evaluator and treating investigator will conduct their MMVS assessments using a photographic scale (Appendix 2).

**Table 3. Medicis Midface Volume Scale**

MMVS	
1	Fairly full midface; cheek prominence projected beyond the infraorbital rim at 45-degree view.
2	Mild loss of fullness in midface area; flatness of midface; cheek prominence at or behind infraorbital rim. May have slight presence of tear trough but not extending past mideye. Can start to see minimum volume loss of anterior cheek.
3	Moderate loss of fullness with slight hollowing below malar prominence; presence of the nasojugal groove extending past mideye.
4	Substantial loss of fullness in the midface area, clearly apparent hollowing below malar prominence; evidenced by significant indentation in the midface area.

 GALDERMA	Title 43CHSA1803 Clinical Study Protocol	Doc id MA-39381
--	--	---------------------------

#### 7.4 3D Digital Imaging analysis

The measurement of volume change in the midface (right and left combined) from baseline will be calculated by 3D digital image analysis at 6, 9, 12, 18 and 24 months in Group A and Treatment Group, and at 6, 9 and 12 months in Control Group.

#### 7.5 Global Aesthetic Improvement Scale (GAIS)

The 5-graded Global Aesthetic Improvement Scale (GAIS) will be used to assess the aesthetic improvement of the midface fullness of both sides of the live subject as compared to photographs taken before treatment. Each midface side will be rated separately. The treating investigator and the subject will, independently of each other, respond to the question: "How would you describe the aesthetic improvement of the midface fullness for each side today compared to the photos taken before treatment?" GAIS will be assessed by treating investigator and subjects at each follow up visit.

**Table 4. Global Aesthetic Improvement Scale**

Rating	Definition (for treating investigator)
Very much improved	Optimal cosmetic result for the implant in this subject.
Much improved	Marked improvement in appearance from the original condition, but not completely optimal for this subject.
Improved	Obvious improvement in appearance from the original condition.
No change	The appearance is essentially the same as original condition.
Worse	The appearance is worse than the original condition.

#### 7.6 Subject satisfaction questionnaire

Subjects will be asked about their satisfaction with the treatment outcome using a questionnaire at 6, 9, 12, 18 and 24 months in Group A and Treatment Group.

**1). Do you think your Cheek Volume Deficit and/or Contour Deficiency has been improved with the treatment?**

Yes

No

**2). Do you think that the overall result of the treatment looks natural?**

Yes

No

**3). Would you say that the study treatment?**

Surpass your expectations

Meet your expectations

 GALDERMA	Title 43CHSA1803 Clinical Study Protocol	Doc id MA-39381
--	--	---------------------------

- Do not meet your expectations
- You did not have any specific expectations before the injections

**4). Do you think that the treatment brings you more?**

**(tick all boxes that apply)**

- Youth
- Beauty
- Harmony
- Symmetrical appearance
- Pep/Liveliness/Freshened look
- Self esteem /confidence

**5). Would you say that you feel more attractive?**

- Yes
- No

**6). How do you feel about yourself since the treatment was performed?**

- Very much better
- Much better
- Somewhat better
- The Same
- Worse; if worse, please explain why:

**7). Overall, how satisfied are you with the treatment result?**

- Very satisfied
- Satisfied
- Somewhat satisfied
- Not satisfied

**8). Did you get any feedback about your look from your family, friends, colleagues?**

- Positive feedback
- Negative feedback
- No feedback

**9). Would you recommend this treatment to friends?**

- Yes
- No

**10). Would you like to receive the same treatment again?**

 GALDERMA	Title 43CHSA1803 Clinical Study Protocol	Doc id MA-39381
--	--	---------------------------

- Yes, exactly the same
- No ; if no, please explain why \_\_\_\_\_.

## 8 Safety Assessments

### 8.1 Anticipated injection related reactions

The subjects of for Group A and Treatment Group will evaluate anticipated injection related reactions, i.e. pain, tenderness, localized redness, bruising, hematoma and edema, which generally resolve within 2-6 days. The subject will be instructed by the Investigator to record pain, tenderness, localized redness, bruising, hematoma, edema and other daily for evaluation of these events in 4-week diaries after each treatment session. The presence and maximum intensity of the symptoms will be recorded for the treated area (table 5). The treating Investigator will review the diary at the next visit after each treatment and if necessary, appropriate intervention (treatment or procedure) will be carried out at the discretion of the Investigator. If required, the Investigator can also decide that the subject's participation in the study should be terminated.

**Table 5. Grading for pain, tenderness, localized redness, bruising, hematoma, edema and other, in the subject diary**

None	
Mild	Awareness of symptoms or signs, but easily tolerated (acceptable)
Moderate	Enough discomfort to interfere with usual activity (disturbing)
Severe	Incapacity to work or to do usual activity (unacceptable)

### 8.2 Laboratory assessment

Laboratory samples for Haematology and Serum chemistry assessment will be taken at the screening visit (day -21 to day 1) for all subjects. In Group A and Treatment Group, it will also be taken at 12 months visit or at early termination if termination occurs before 12 months visit.

The following laboratory assessments will be performed:

- Haematology: haemoglobin, red blood cells, white blood cells, differential count and platelet count.
- Serum chemistry: renal function tests (creatinine and BUN); and liver function tests (aspartate amino transferase (ASAT), alanine amino transferase (ALAT) total bilirubin, direct bilirubin and indirect bilirubin).

Pregnancy test (Urine HCG) will be performed at screening, all injection visits (prior to treatment and the study completion/early termination for Group A and Treatment Group, and at screening for Control group, in all women of childbearing potential, including those currently using contraception. The test result must be negative for the subject to receive any treatment with study product.

Other laboratory test might be performed at the discretion of the investigator. All laboratory assays will be performed at a local laboratory. Reference ranges will be supplied by the

 GALDERMA	Title 43CHSA1803 Clinical Study Protocol	Doc id MA-39381
--	--	---------------------------

Effective date: 2019-06-20 00:56

Effective

Version: 2.0

laboratory and used by the Investigator to assess the laboratory data for clinical significance and out of range pathological changes.

The results of the hematology and serum chemistry will only be used for safety assessment by investigator and will not be collected in the eCRF. The pregnancy test for women of childbearing potential will be recorded in the eCRF.

### 8.3 Adverse Events

#### 8.3.1 Definition of Adverse Events

An AE is any untoward medical occurrence, unintended disease or injury, or untoward clinical signs (including abnormal laboratory findings) in subjects, users or other persons\*, whether or not related to the study product.

This definition includes:

- events related to the investigational product or the reference product
- events related to the procedures involved

\*For users or other persons, this definition is restricted to events related to the investigational product

#### 8.3.2 Definition of Serious Adverse Event

A serious adverse event (SAE) is an AE that:

- a) led to death,
- b) led to serious deterioration in the health of the subject, that either resulted in
  1. a life-threatening\*\* illness or injury, or
  2. a permanent impairment of a body structure or body function, or
  3. in-patient or prolonged hospitalisation\*\*\*, or
  4. medical or surgical intervention to prevent life-threatening illness or injury or permanent impairment to a body structure or a body function,
- c) led to foetal distress, foetal death, or a congenital abnormality or birth defect

In cases of doubt, whether an AE fulfils a serious criterion or not, there should be a predisposition to report as a SAE rather than not report as such (see section 8.4.4).

\*\*The term "life-threatening" in the definition of "serious" refers to an event in which the patient was at risk of death at the time of the event; it does not refer to an event which hypothetically might have caused death if it were more severe. (Source: ICH-E2A clinical safety data management: definitions and standards for expedited reporting).

\*\*\* Planned hospitalisation for a pre-existing condition, or a procedure required by the CSP, without serious deterioration in health, is not considered a SAE. (Source: ISO14155:2011).

#### 8.3.3 Recording Instructions

AE will begin to be collected after ICF signed. Each subject will be questioned about AEs at each clinical visit following the screening visit. The question asked will be "Since your last clinical visit have you had any health problems?" Information on AEs can also be obtained from signs and symptoms detected during each examination or from a laboratory test,

	
Title 43CHSA1803 Clinical Study Protocol
	
Doc id MA-39381

--	---	----------------------------

2019-06-20 00:56

Effective date:

Effective

Version: 2.0

observations by the study personnel, subject diaries or spontaneous reports from the subjects.

The Investigator will assess the presence of any papules (<5mm in diameter) or nodules (≥5mm in diameter). If present, the papules/nodules will be recorded as AE and should be further assessed as visible/non-visible and inflammatory/non-inflammatory.

When an AE is related to a device deficiency (refer to section 8.4), including technical device malfunction, the AE shall be recorded on the AE module in the eCRF and the technical complaint shall be reported separately on the clinical study complaint form.

Investigators, or other study personnel, will record all AEs in the eCRF, including:

- Event term (recorded in standard medical terminology and avoiding abbreviations),
- Description of event and affected area (if applicable),
- Start date (First day with symptoms)
- Stop date (Last day with symptoms)
- Intensity (mild, moderate or severe according to definition in section 8.3.3.1)
- Seriousness (serious or not serious, according to definition in section 8.3.2)
- Causal relationship to study product and study product injection procedure (yes or no)
- Action taken (none, medication treatment, non-pharmacological treatment or other procedures/ tests, subject withdrawn)
- Outcome of the AE (ongoing, recovered, recovered with sequelae, death, chronic/ stable, not recovered at study end)

The AE module in the eCRF must be signed and dated by the Investigator.

### 8.3.3.1 *Intensity*

For each reported AE, the intensity will be recorded. The following definitions of intensity are to be used:

- Mild:** A mild AE means awareness of symptoms or signs, but easily tolerated (acceptable).
- Moderate:** A moderate AE means enough discomfort to interfere with usual activity (disturbing).
- Severe:** A severe AE means incapacity to work or to do usual activity (unacceptable).

If the intensity changes over time the maximum intensity of the AE should be recorded.

### 8.3.3.2 *Causal Relationship and Seriousness*

Each AE, serious as well as non-serious, will be assessed by the Investigator for causal relationship with the study product and its use (the injection procedure) and for seriousness (yes or no) of the event.

 GALDERMA	Title 43CHSA1803 Clinical Study Protocol	Doc id MA-39381
--	--	---------------------------

2019-06-20 00:56

Effective date:

A two-point scale (Yes or No) will be used for causality assessments. The Investigators shall be asked to indicate a response to each of the following questions in the eCRF:

- “Do you consider that there is a reasonable possibility that the event may have been caused by the study product?” and
- “Do you consider that there is a reasonable possibility that the event may have been caused by the study *product injection procedure*?”

If any of these questions is answered Yes, the AE is considered related.

Each AE will also be assessed for causal relationship and seriousness by the Sponsor, in order to fulfil regulatory requirements.

#### 8.3.4 Reporting of Adverse Events

AE reporting on each subject will start after the ICF has been signed. The reporting will continue during each follow-up visit (including telephone contacts and extra visits between planned visits) until the last scheduled visit in the study.

**All AEs**, non-serious as well as serious, are to be reported as an AE in the eCRF.

#### 8.3.5 Reporting of Serious Adverse Events

After becoming aware of any SAE, the Investigator shall report it to his/her administrative department of medical device clinical trials under the clinical trial institution, which in turn shall notify the Sponsor Representative in writing. This initial report can be made via fax or e-mail or submitted via the eCRF.

In case of difficulty to obtain all the required information within 24 hours, an initial report can be submitted, with the following information as a minimum, irrespective of whether some of it is regarded as preliminary:

- CTN
- Subject identification (age, gender, subject number)
- AE description
- date when AE occurred
- date when AE became serious
- Name of PI and original reporter (if other than Investigator)
- Name of study product
- Treatment specification

The Investigator will assure completeness of the SAE information and the supporting documentation.

Follow-up information and data missing in the initial SAE reporting shall be gathered as soon as possible and reported to the Sponsor via Sponsor's representative immediately but not later than 24 hours of awareness of the new data. Complete and adequate information on each SAE is required. All attempts to obtain this information, including dates for follow-up activities, must be documented by the Investigator.

Effective

Version: 2.0

 GALDERMA	Title 43CHSA1803 Clinical Study Protocol	Doc id MA-39381
--	--	---------------------------

### **Supporting documentation to be provided with the SAE report:**

- Concomitant Medication Form/list
- Concomitant Procedure/Treatment Form/list
- AE Form/list
- Medical History Form/list
- Any other relevant supporting documentation (e.g. hospital notes, death certificate, autopsy reports etc.)

---

**Fax number for SAE reporting:** [contact]

**E-mail for SAE reporting:** [contact]

**Surface mail for providing complementary information:**  
Q-Med AB  
Attn. Corporate Medical Affairs & Vigilance  
[name]  
[name]

**E-mail for Device deficiency, Clinical Study Complaint Form:** [contact]

---

E-mail address will be pre-programmed in the eCRF system.

For non-urgent complementary information not possible to send by e-mail or fax, please use surface mail.

The SAE form (NMPA template in Chinese) must be signed and dated by the Investigator. If the initial 24-hour SAE report does not contain full information or if it is made without using the SAE form, the fully completed and signed SAE form shall be e-mailed or faxed to the Sponsor (contact details refer to 24-hour contact person list in ISF). A copy of the fully completed SAE form shall be kept at the site.

In addition, according to national regulations, the investigator will report a SAE Form (NMPA SAE template) to the administrative department of medical device clinical trials in his/her hospital, and they should, within 24 hours, deliver a written report to the corresponding Ethics Committee and the local food and drug administrative department of province, autonomous region and municipality at the place where the clinical trial institution locates. In case of a death incident, the clinical trial institutions and investigators should furnish the Ethics Committee and the Sponsor Representative with all required materials.

The Sponsor Representative is responsible for, within five (5) business days upon being informed, reporting any SAE or device defect with the likelihood of SAE to Shanghai Municipal FDA and Shanghai Municipal Health Commission by fax or mail. The relevant correspondence will be documented in TMF; meanwhile, the Sponsor Representative should notify other clinical trial institutions and investigators participating in the study, and promptly report it to

 GALDERMA	Title 43CHSA1803 Clinical Study Protocol	Doc id MA-39381
--	--	---------------------------

the Ethics Committee of the involved clinical trial institutions via the administrative department of medical device clinical trials according to national regulations.

### 8.3.6 Follow-up of Unresolved Events after study termination and new Events after study termination.

All serious as well as non-serious AEs with a causal relationship to the study product or treatment procedure and ongoing at study end, shall be followed up after the subject's participation in the study is over. Such events shall be followed-up after the last study visit until resolved, assessed as chronic or stable, or for at least three months. Final outcome after study end should be reported on a paper AE form.

All serious as well as non-serious AEs with a causal relationship to the study product or treatment procedure with onset after subject participation in the study has ended shall be collected and reported to Sponsor on a paper AE form or in the post marketing AE form or SAE paper form if applicable. The events shall thereafter be followed up until resolved or considered chronic or stable, or for at least three months. Final outcome shall be reported on the AE follow up form or in the post marketing AE form. The Investigator shall report any such AE or SAE including all previous Adverse events reported during the study and medical history of the patient to the Sponsor immediately but not later than 24 hours of awareness of the event. This report can be made via fax or e-mail according to contact details specified in section 8.3.5.

### 8.3.7 Pregnancy

Pregnancy itself is not regarded as an AE.

If there is a pregnancy during the study period the subject must continue to be followed within the study and the outcome of pregnancy must be reported even if the expected date of delivery occurs after study completion.

A pregnancy confirmed during the study period must be reported by the Investigator on a pregnancy report form immediately upon acknowledgement be submitted to the Sponsor according to contact details specified in section 8.3.5. The report can be prospective or retrospective. Follow-up shall be conducted to obtain outcome information on all prospective reports.

Cases that led to foetal distress, foetal death or a congenital abnormality or birth defect are to be regarded as SAEs and shall be reported on the exposure *in utero* report form to the Sponsor immediately but no later than 24 hours after the Investigators awareness. These events shall be handled as SAEs during data processing. Other complications during the pregnancy that are related to the pregnant woman and fulfils any serious criteria, such as pre-eclampsia requiring hospitalisation, shall be reported and handled as SAEs. Elective abortions without complications will not be reported as AEs.

### 8.3.8 Anticipated Adverse Events

Information regarding anticipated AEs below is also included in the Sculptra Investigators Brochure.

Subcutaneous papules/, invisible but palpable or visible nodules including periorbital nodules, or areas of induration have been noted in the injection area. Nodules are occasionally

 GALDERMA	Title 43CHSA1803 Clinical Study Protocol	Doc id MA-39381
--	--	---------------------------

Effective date: 2019-06-20 00:56

**Effective**

Version: 2.0

associated with inflammation or discolouration. The early occurrence of subcutaneous nodules at the injection site (within 3–6 weeks after treatment) may be minimised by adhering to proper dilution and injection techniques. Delayed occurrences of subcutaneous nodules at the injection site (within 1–14 months post injection) have been reported with sometimes a prolonged duration of up to 2 years. Improper injection techniques such as superficial placement, excessive amount of product or incorrect reconstitution may lead to appearance of papules or nodules at the injection site. Massaging the treatment area to ensure proper distribution of the product may minimise the appearance of such papules or nodules.

For nodular areas or late granuloma formation, in some cases, they resolved spontaneously or following treatment with multiple intralesional injections of corticosteroids and/or antineoplastic agents (e.g. 5-fluorouracil). Surgical excision of the nodules was sometimes required when they were larger in size, occurring in difficult anatomical regions (e.g. lower eyelid) or persisting after other treatments.

This product must not be injected intramuscularly or intravascularly. Localised superficial necrosis and scarring may occur after injection in or near vessels. It is thought to result from the injury, obstruction, or compromise of blood vessels. Special caution should be taken if the patient has undergone a prior surgical procedure in the planned treatment area. Areas with limited collateral blood flow has an increased risk of ischaemia. Aspiration prior to injection is recommended.

Unintentional introduction of soft tissue fillers into the vasculature in the face may lead to embolisation, occlusion of the vessels, ischaemia, necrosis or infarction at the implant site or in the area supplied by the blood vessels affected. Rare but serious adverse events include temporary or permanent vision impairment, blindness, cerebral ischaemia or cerebral haemorrhage leading to stroke, skin necrosis, and damage to underlying facial structures. Immediately stop the injection if any of the following symptoms occurs, including changes in vision, signs of a stroke, blanching of the skin, or unusual pain during or shortly after the procedure. Patients should receive prompt medical attention and possibly evaluation by an appropriate health care practitioner specialist, should an intravascular injection occur.

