#### Treatment

Each subject assigned to Group A and Treatment Group will receive up to 4 injection sessions with 5( $\pm 1$ ) weeks (at least 4 weeks) intervals. Initial treatment will be on Day 1. Study treatments should be stopped if optimal midface augmentation has been obtained or a maximum of 4 injection sessions completed. Optimal midface augmentation is defined as the best possible aesthetic result that can be obtained for an individual study participant, as agreed upon by the treating investigator and subject.

Subjects assigned to the Control Group will not receive treatment during the study.

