#### 4.7 Schedule of events

**Table 1. Schedule of Events for Group A and Treatment Group**

	Screening	Baseline / Treatment 1	Treatment 2 (Optional) b	Treatment 3 (Optional) b	Treatment 4 (Optional) b	Follow-up	Follow-up	Final visit / Early termination
	D-21 to D1	D1	5W( $\pm 1w$ ) after treatment 1	5W( $\pm 1w$ ) after treatment 2	5W( $\pm 1w$ ) after treatment 3	5W( $\pm 1w$ ) after Last treatment	6M ( $\pm 2w$ ), 9M ( $\pm 2w$ ), 12M ( $\pm 2w$ ), and 18M ( $\pm 3w$ ) after Baseline	24M ( $\pm 4w$ ) after Baseline
Informed consent	X							
Demography	X							
Height		X						
Weight		X					X	X
Medical history & concurrent diseases	X	X a						
Concomitant medication/procedures	X	X a	X	X	X	X	X	X
Vital signs		X c						
Laboratory tests	X						X d	X e
Pregnancy test for childbearing potential women	X	X a,c	X c	X c	X c			X
Inclusion and Exclusion criteria	X	X a						
Randomization		X						

Treatment		X	X	X	X			
MMVS (Blinded Evaluator)	X	X a,c					X	X
MMVS (treating investigator)	X	X a,c	X c	X c	X c	X	X	X
Photography		X c	X c	X c	X c	X	X	X
GAIS (Treating investigator and Subject)			X c	X c	X c	X	X	X
Subject satisfaction questionnaire							X	X
Dispense subject diary		X	X	X	X			
Review and collect subject diary			X	X	X	X		
Device deficiencies		X	X	X	X			
Assessment of AE	X	X a	X	X	X	X	X	X
Study termination								X

- a) Omitted if screening and baseline visit occur on the same day.
- b) The visit is omitted if optional treatment was not performed.
- c) Performed prior to treatment.
- d) Only performed at 12M.
- e) Only performed at early termination if termination occurs before 12M visit.

	
Title 43CHSA1803 Clinical Study Protocol
	
Doc id MA-39381

--	--	-----------------------------------

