#### 4.8.1.3 Optional treatment 2, 3, and 4 (only for subjects who receive the treatment)

- Photography (before treatment)

 GALDERMA	Title 43CHSA1803 Clinical Study Protocol	Doc id MA-39381
--	--	---------------------------

Effective date: 2019-06-20 00:56

- MMVS (before treatment, by treating investigator)
- GAIS (before treatment, by treating investigator and subject)
- Pregnancy test for childbearing potential women (before treatment)
- Treatment
- Collect and review subject diary
- Dispense subject diary
- Concomitant medications/procedures
- Device deficiencies
- AE since last visit

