1.1 Background

1.1.1 Study design

This is a randomized, multi-center, evaluator-blinded, no-treatment controlled study of Sculptra for correction of Midface Volume Deficit and/or Midface Contour Deficiency in subjects of Chinese origin, men or women aged 18 years or older.

For Group A, after screening, eligible subjects will be treated from day 1 and followed up for 24 months.

For Group B, the study includes two phases as follows:

Main study phase: It is randomized, evaluator-blinded and no-treatment controlled. After screening, all eligible subjects will be randomized either to the Treatment Group or the Control Group in a 2:1 ratio. All the subjects will be followed up for 12 months.

Extension study phase: After the main study phase, the Treatment Group and Group A will be followed up for additional 12 months.

Each Treating Investigator will enroll 1 or 2 subjects as Group A. Before start of enrolment into Group B, the injection technique will be evaluated by the Sponsor or designee of Sponsor and performed after the subjects in Group A for each investigator have received their first treatment and second treatment. If treatments are found to be correctly performed, no further training is needed, there are no outstanding questions regarding the injection technique and no other corrective actions are identified, the enrolment in Group B can start for that investigator.

Each subject assigned to Group A and Treatment Group will receive up to 4 injection sessions with 5 (± 1) weeks intervals. Study treatments should be stopped if optimal midface augmentation has been obtained or a maximum of 4 injection sessions completed. Optimal midface augmentation is defined as the best possible aesthetic result that can be obtained for an individual study participant, as agreed upon by the treating investigator and subject.

Subjects assigned to the Control Group will not receive treatment during the study.

For more details regarding the study, and references, see the Clinical Study Protocol (MA-39381).

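### SAP 2.5.3 counts AE onset by calendar date only, so an event found just before a re-injection and dated that day scores as day 0 of the new session

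*Protocol*

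**What the plan says.** **Timing.** Protocol 8.3.8 (and 2.6) refers to "The early occurrence of subcutaneous nodules at the injection site (within 3–6 weeks after treatment" and, separately, to delayed nodules at 1 to 14 months. SAP 1.1.1 allows "up to 4 injection sessions with 5 (± 1) weeks intervals", and Protocol 4.1 adds "weeks (at least 4 weeks) intervals".

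**Order within the visit.** At Treatments 2 to 4, Table 1 gives footnote c ("Performed prior to treatment") to four rows: the pregnancy test, the treating investigator's MMVS, photography and GAIS. Section 4.8.1.3 tags the same four items, for example "GAIS (before treatment, by treating investigator and subject". Diary review and AE assessment carry no such tag in either place. In 4.8.1.3 the entry "Collect and review subject diary" stands untagged below the treatment item, and the AE entry comes last. Section 8.1 states "The treating Investigator will review the diary at the next visit after each treatment", which is the re-injection visit whenever another session is given. Section 8.3.3 requires assessment for papules and nodules but sets no time for it.

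**Derivation.** SAP 2.5.3 defines time to onset as the AE start date less the date of the latest treatment. A missing start date is set to the day of the latest treatment. The SAP plans related AEs by session (Table 3-46), time to onset from last treatment (Table 3-47), and a listing of related AEs with onset more than 21 days after the latest treatment.

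**The concern.** A re-injection visit is a natural time to discover an early nodule from the previous session. The subject is examined at 4 to 6 weeks, inside the window that the protocol names, and is then injected on the same date. A derivation that uses dates alone cannot tell an event already present that morning from one caused by that day's injection. It credits both to the new session.

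Nodules and papules are the product-specific risk that the protocol describes at most length, and time to onset is part of the first safety endpoint. An early nodule recorded as an immediate reaction to the next injection distorts the onset pattern and the per-session counts. It also leaves the listing intended to show late events.

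**Working it through.** No figure in the plan needs reproducing. The check compares the windows and then applies the SAP formula.

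**1. Windows.** Early nodules: 3 × 7 = 21 to 6 × 7 = 42 days. Re-injection: (5 − 1) × 7 = 28 to (5 + 1) × 7 = 42 days. The second range lies wholly inside the first. The share of the nodule window already elapsed is (day − 21) / 21.

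| Re-injection at | Day | Share of nodule window elapsed | Days since a 28-day diary ended |
|---|---|---|---|
| 4 weeks | 28 | 7/21 = 1/3 | 0 |
| 5 weeks | 35 | 14/21 = 2/3 | 7 |
| 6 weeks | 42 | 21/21 = 1 | 14 |

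**2. SAP formula for an event dated on the visit day.** Take the previous session as day 0 and the re-injection as day 35, with a nodule found before the injection and dated day 35.
- From the session that preceded it: 35 − 0 = 35 days, which exceeds 21, so it is listed as late onset.
- By SAP 2.5.3, with that day's injection as the latest treatment: 35 − 35 = 0 days, so it is not listed.

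Over the permitted interval the understatement is 28 to 42 days. Every such related event should pass the 21-day cut, since 28 > 21, and none does.

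**3. Event with an earlier recorded start date.** Symptoms begin on day 25 and are reported on day 35. The latest treatment at day 25 is day 0, so onset is 25 − 0 = 25 days. The session is right and the event is listed. There is no error here.

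**4. Event with no start date.** If the latest treatment is taken as the one given at the visit, the imputed onset is again day 0 of the new session, although the event was seen before that injection. The session is wrong. The true onset is unknown, so its place in the 21-day listing cannot be settled. The same imputed date enters the duration in Table 3-48.

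**5. Can the date rule be reread to avoid this?** If latest treatment meant strictly before the start date, a genuine reaction on the day of re-injection would score 28 to 42 days, and one on Day 1 would have no treatment to count from. A rule on dates alone fails one way or the other. The AE items listed in Protocol 8.3.3 include start and stop dates but nothing that places a same-day event before or after the injection.

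**6. Exposure.** There are at most three re-injection visits per subject: 3 × 126 = 378 in the Group B Treatment Group and 3 × 32 = 96 in Group A, 474 in all. This is a ceiling that assumes four sessions for everyone; the two groups are summarised separately. It counts visits and says nothing about the number of affected events.

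**The case against.** A reader might infer that the protocol has safety review follow the injection, because the tagged items are mostly effectiveness ratings and the diary and AE entries stand below treatment in 4.8.1.3. The documents do not support that.

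- The lists are inventories. Table 1 places the treatment row above MMVS, photography and GAIS, all of which are tagged as earlier. Section 4.8.1.2 lists randomization ahead of the baseline pregnancy test and MMVS.
- A missing tag does not imply a later time. Eligibility and randomization carry no footnote c at baseline, yet must precede injection. Concomitant medication is untagged at Treatments 2 to 4, although Protocol 4.6 restricts some drugs in the two weeks before treatment.
- Section 8.1 ties diary review to intervention or termination of participation at the investigator's discretion.
- Safety-relevant checks do come first: the pregnancy test, photographs (which section 7.2 also uses to document AEs) and ratings of both cheeks. A visible nodule could be noticed then. A palpable but invisible one, which the protocol also describes, need not be.

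All of this stands. The order is left open, and no two passages contradict each other on it. It is also fair that the overlap of windows is unremarkable, given delayed nodules at 1 to 14 months, and that section 8.3.3 defines the start date as the first symptomatic day, which protects most events that the subject had already noticed.

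The objection does not remove the same-day case. A nodule first detected at the visit may well be dated that day, and SAP 2.5.3 then gives day 0 even at a site that reviewed everything first. For the same reason, a visit-order tag alone would not cure it.

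**Conclusion.** The point holds as a minor defect in the SAP derivation, made more likely to matter by the protocol's silence on order within the visit. For an event found before re-injection and dated that day, onset is understated by 28 to 42 days, the session is wrong, and a related event is lost from the late-onset listing. For an undated event, the session can be wrong and the onset cannot be recovered.

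This rests on three assumptions: that an injection on the AE start date counts as the latest treatment; that Table 3-46 assigns sessions on the same basis, since the SAP gives no separate rule; and that some events are dated on the visit day or left undated. The documents give no count of such events, so the overall effect on the tables cannot be sized. The primary effectiveness analysis is not touched.

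It would be too strong to conclude that sites are directed to inject before reviewing safety, or that the injection interval is wrong. The documents show neither.

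**What to change.** **SAP 2.5.3.** Add one sentence: for an event already present before an injection given on the same day, onset and session are counted from the previous treatment. State also how an undated event of this kind is shown. Its session is the previous one, but its onset is unknown, so the SAP should say whether an imputed value is tabulated or the onset is reported as missing. SAP 2.1 provides for amendment before database lock.

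**Protocol.** Reconcile 4.8.1.3 and Table 1 with 8.1 and 8.3.3, so that diary and AE data since the last visit are recorded at Treatments 2 to 4 as pre-injection data, using the existing footnote c. AE recording stays open afterwards for events during or after the injection. This concerns only when data are recorded; whether to inject is left as the protocol has it.

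**Cost.** One SAP sentence with its note on undated events, two tags, and one item on the AE record showing whether a same-day event came before or after the injection. That item is the only added burden. No visit or procedure is added.
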